#### *10.1.3.2 mRNA expression profile signature positive and negative PSA50 response calculations:*

Similarly to above, subjects will have tumor tested with RNA expression profiling and scored for likelihood for response to rucaparib per the Decipher GRID platform (GenomeDx). For subjects considered to have a positive RNA expression signature based upon a binary score assigned via the GenomeDx proprietary algorithm, a PSA50 response rate will be calculated. Similarly, a calculation will be performed for subjects considered to have a negative RNA expression signature.

#### *10.1.3.3 PARP-1, PARP-2, $\gamma$ H2AX, RAD51, 53BP1 mRNA/protein levels:*

Subjects will have pretreatment and on-treatment tumor specimens analyzed. IHC and RNA in situ hybridization staining PARP-1 and PARP-2 will be performed on the pretreatment samples and scored on scale of 0 (none) to 3 (intense staining), and the results will be associated with responses for both proteins, separately, using descriptive statistics and Fisher's Exact Tests. Immunofluorescence will be used to quantify the median intensity of each  $\gamma$ H2AX, RAD51 and 53BP1 foci per cell as well determine the median number of foci per cell on the pretreatment biopsies. Using analytical microscopy, Drs. [name] and [name] have developed imaging software, which can isolate single nuclei and quantify both the intensity and number of immunofluorescent foci per nucleus (i.e. per cell). Using FFPE tissue obtained at biopsy, we will examine the change in DNA damage foci number and intensity (reported as median percent change) induced by PARPi in PSA50 responders versus non-responders using a T-test.

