### Exploratory Endpoints

- PSA50 response, defined as decline in PSA to ≥50% of baseline level, confirmed with a second measurement at least 4 weeks later, in patients with and without a loss-of-function mutation or total allelic loss of second (somatic) gene allele (i.e. biallelic inactivation) (In patients who undergo biopsy or with archival tissue available).
- To associate PSA response to rucaparib with changes in gamma-H2AX, RAD51, 53BP1 formation in tumor tissue compared to baseline (In M1 patients who undergo biopsy).
- To associate mRNA expression array signature with PSA response (In M1 patients only who undergo biopsy).
- To associate PSA response to rucaparib with baseline PARP-1 and PARP-2 protein and mRNA expression levels in baseline tumor biopsy specimens or archived tissue.
- To associate the incidence of reversion mutations with clinical progression.

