#### 8.3.2 *PSA*

For each patient, use a waterfall plot to report the percent change in PSA from baseline to 12 weeks (or earlier for those who discontinue therapy) and the maximum decline in PSA that occurs at any point after treatment. We will also report the proportion of patients to achieve a 50% of greater decrease in PSA from baseline (i.e. PSA50 response rate)

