**10. STATISTICAL CONSIDERATIONS**

The primary endpoint will be the proportion of subjects who achieve a PSA response, defined as a 50% or greater decline in PSA from baseline, confirmed on a subsequent

measurement at least 3 weeks apart. The treatment regimen would be considered of insufficient activity for further study in this population if the PSA response rate is 50% or less. The sample size is calculated to detect an improved PSA response rate from 50% to 75%. An optimal Simon two stage design is planned. A total of 12 patients will be entered in the first stage with a planned analysis for futility performed 12 weeks after the last patient began rucaparib. The number of patients allowed with a non-BRCA1, -BRCA2, or -ATM mutation in stage 1 will be capped at 3. If 6 or fewer subjects have a PSA response, the study will be terminated and we will conclude the regimen is ineffective. If  $\geq 7$  subjects respond, then an additional 16 patients will be studied, for a total of 28 patients. If a total of 17 or fewer subjects respond in stage one and two combined, we consider this regimen ineffective. If a total of 18 or more respond, we conclude the regimen is promising and warrants further study. The maximum sample size will be increased to 30 patients to account for possible dropouts. The total number of patients (stage 1 and 2) allowed with a non-BRCA1/ -BRCA2 mutation will be capped at 10; this will ensure that at least 20 men will be enrolled with germline BRCA1/BRCA2 mutations.

This design provides 90% power to detect an absolute 25% increase in PSA response rate with a one-sided type I error of 0.1. The probability of early stopping is 0.61 under the null hypothesis that the PSA Response Rate is 50%.

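### Section 10.1.3.3 tests foci change and PARP scores only against categorical response, although each man's PSA change is already planned; for foci change this may cost power

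*Combined protocol and SAP*

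**What the plan says.** Section 10.1.3.3, repeated in the Synopsis under Exploratory Analyses, specifies two tested analyses of tissue markers.

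- **Foci change** (gamma-H2AX, RAD51, 53BP1): change in number and intensity "induced by PARPi in PSA50 responders versus non-responders using a T-test".
- **PARP-1 and PARP-2 staining**, scored 0 to 3 on pretreatment tissue: associated with responses by descriptive statistics and Fisher's exact tests. The section does not define responses. The Synopsis endpoint reads "To associate PSA response to rucaparib with baseline PARP-1 and PARP-2 protein and mRNA expression levels" and does not name PSA50 either.

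Two other marker analyses have no test. Section 10.1.3.1 (biallelic status) gives PSA50 rates with confidence intervals for hypothesis generation. Section 10.1.3.2 (mRNA signature) gives PSA50 rates by signature group.

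Section 8.3.2 says, for each patient, to "use a waterfall plot to report the percent change in PSA from baseline to 12 weeks" (or earlier for men who stop), and also to report the maximum decline. None of Sections 10.1.3.1 to 10.1.3.3 uses these values.

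Study biopsies are for metastatic patients only. The on-treatment biopsy is optional, at C4D1 (Table 1, footnote e; Section 5.2.2). The documents give no expected number of pairs, and no alpha, effect size or power for any marker analysis.

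**The concern.** A yes/no split treats a 51% and a 99% PSA decline as the same result, and a 49% and a 51% decline as opposite results. That is acceptable for a decision rule. It is costly when the aim is to learn whether a marker moves with response and few men supply tissue.

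Foci change needs two biopsies from the same man, so its sample will be smaller than the trial's maximum of 30. At the design response rate of 75%, the non-responder group would be a quarter of that sample. Another two-group test does not help, because the information is lost when the outcome is split. At stake is how much the trial learns from biopsies taken for this purpose.

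**Working it through.** **1. The plan's own power figure.** The only one is for the primary endpoint (Section 10): "The sample size is calculated to detect an improved PSA response rate from 50% to 75" per cent, with 12 men in stage one, stopping at 6 or fewer responders, and 28 in total, with 18 or more needed.

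- Early stopping under 50%: P(X ≤ 6 | 12, 0.5) = (1+12+66+220+495+792+924)/4096 = 2510/4096 = 0.613. Stated: 0.61.
- Exact two-stage power at 75%: 0.902. Stated: 0.90.
- Exact one-sided error at 50%: 0.081, within the stated 0.10.

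The design reproduces, and this point does not touch it. Its 50% and 75% serve below as the range for the responder share.

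**2. Timing.** C4D1 falls 3 × 28 = 84 days after C1D1, which is week 12. The 12-week PSA change therefore matches the second biopsy in time.

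**3. Group sizes.** The number of pairs is an assumption. With 16 pairs and 75% responders, 16 × 0.25 = 4 non-responders are expected. With 10 pairs, the chance that one group is empty is 0.75^10 + 0.25^10 = 0.056.

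**4. Large-sample cost of the split.** If PSA50 is a cut of a normal outcome with responder share p, the split's efficiency relative to the continuous outcome (weak correlation) is φ(z_p)² / [p(1−p)].

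- p = 0.50: 0.3989² / 0.25 = 0.64
- p = 0.75: 0.3178² / 0.1875 = 0.54

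**5. Small-sample cost for foci change.** Simulation with 40,000 trials per cell. Assumed, not in the documents: bivariate normal marker and PSA change, their correlation, PSA50 as an exact cut of that PSA change, and two-sided 0.05. The pooled t-test on the split is compared with Spearman's correlation using permutation critical values. A trial with an empty group counts as no rejection. Entries are power in per cent at 50 / 65 / 75% responders; gains are taken before rounding.

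| Pairs | Correlation | t-test on split | Spearman | Gain (points) |
|---|---|---|---|---|
| 6 | 0.5 | 11.7 / 10.8 / 9.5 | 9.9 / 9.8 / 9.9 | −1.7 / −1.0 / 0.4 |
| 6 | 0.6 | 15.2 / 14.0 / 12.0 | 13.9 / 14.2 / 14.4 | −1.4 / 0.2 / 2.4 |
| 8 | 0.5 | 16.1 / 15.2 / 13.1 | 18.8 / 19.2 / 18.8 | 2.8 / 4.0 / 5.7 |
| 8 | 0.6 | 22.5 / 21.2 / 17.8 | 27.9 / 27.8 / 27.5 | 5.4 / 6.5 / 9.7 |
| 12 | 0.5 | 25.3 / 24.0 / 21.4 | 33.5 / 33.2 / 33.1 | 8.2 / 9.2 / 11.7 |
| 12 | 0.6 | 37.4 / 35.2 / 30.4 | 48.8 / 49.1 / 48.7 | 11.4 / 13.9 / 18.3 |
| 16 | 0.5 | 34.8 / 32.5 / 28.9 | 46.0 / 45.8 / 45.9 | 11.2 / 13.4 / 17.0 |
| 16 | 0.6 | 50.0 / 47.5 / 41.3 | 64.5 / 65.2 / 64.4 | 14.6 / 17.8 / 23.1 |
| 20 | 0.5 | 43.5 / 41.1 / 36.4 | 57.4 / 57.3 / 57.2 | 13.9 / 16.2 / 20.8 |
| 20 | 0.6 | 61.2 / 57.9 / 51.3 | 76.7 / 76.8 / 77.1 | 15.5 / 18.9 / 25.9 |

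At correlation 0.3 the gain is 0.3 to 1.9 points at 8 pairs, 2.4 to 3.7 at 12, and 5.2 to 7.6 at 20. With no correlation, neither test rejects in more than about 5% of trials.

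**6. If the continuous value is not what PSA50 cuts.** Let the PSA value used explain only part (r²) of the response behind PSA50, with correlation 0.5, 65% responders and 16 pairs. The gain is then 8.5 points at r² = 0.9, 4.3 at 0.8, −0.4 at 0.7 and −9.2 at 0.5.

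**The case against.** **The outcomes differ.** This is the strongest objection. Section 10.1.1 counts a confirmed PSA50 decline at any time on rucaparib, whereas a 12-week value is a single unconfirmed measurement that can miss later responses. Step 6 shows that the gain then vanishes at r² of about 0.7 and reverses below that. This stands against using the 12-week value as the main continuous outcome. It is largely met by the lowest on-treatment PSA. Every PSA50 responder has a lowest value at or below half of baseline, and only men whose decline was not confirmed have such a value without being responders.

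**The analyses are exploratory.** They carry no alpha, power target or decision rule, and using the primary-endpoint definition for correlatives is coherent. This stands. It argues for adding an analysis, and against demoting the planned PSA50 comparison.

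**Stronger readings.** A reader might infer that every tissue-marker analysis loses power by a fixed amount. The documents do not support this:

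- Sections 10.1.3.1 and 10.1.3.2 report rates without a test, so there is no power to lose. The post-hoc mRNA work in Section 1.3.3.2 has no stated method.
- For PARP, responses are not defined as PSA50, and the planned test is Fisher's. A loss worked out from another test on PSA50 groups would not describe this plan. Baseline or archived tissue may also cover more men than the paired foci tissue.
- The number of pairs, the correlation and the alpha are all assumed.

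Nor are these markers the trial's only look at mechanism. Section 10.1.3.4 examines reversion mutations in ctDNA without PSA50 groups.

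**Conclusion.** The point holds as a low-severity improvement. The two tested marker analyses in Section 10.1.3.3 use only categorical response, while a more informative outcome is already planned in Section 8.3.2.

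For foci change, the split costs about 3 to 18 points of power at 8 to 12 pairs and 11 to 26 points at 16 to 20. This assumes correlation 0.5 to 0.6, 50 to 75% responders, two-sided 0.05, and PSA50 close to a cut of the continuous change. At 6 pairs the difference lies between about −2 and +2 points. At correlation 0.3 with 8 to 12 pairs it is under 4 points. Within the 8 to 20 pair range the loss is largest at 75% responders, the rate for which the trial is designed.

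For PARP, only the direction of the argument carries over, and no size is claimed. The primary endpoint and its decision rule are unaffected.

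**What to change.** In Section 10.1.3.3 and its Synopsis copy:

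1. Add a rank correlation, with permutation p-value and confidence interval, between each marker and log(lowest on-treatment PSA / baseline PSA). Use Spearman for foci change and Kendall's tau-b for the 0 to 3 PARP scores. Ranks suit a percent change that is bounded at −100% and skewed; the log does not alter them and only helps plotting.
2. Repeat it with the 12-week (or earlier stop) ratio as a sensitivity analysis.
3. Keep the planned PSA50 comparison alongside, and state which outcome responses means in the PARP analysis.
4. Report the number of men in each analysis.

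The cost is wording only: no new data, visits or patients. The downside is one more exploratory result per marker, which is not on the primary-endpoint scale.

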Objectives	Primary

To estimate the PSA50 response rate to rucaparib in patients with metastatic and non-metastatic prostate cancer that harbor an inactivating mutation in a homologous recombination DNA repair gene while on treatment with rucaparib, defined as a decline in PSA to 50% of baseline level, confirmed with a second measurement at least 4 weeks apart (PCWG3).

Secondary

- To estimate the median PSA progression-free survival (PCWG3).
- To estimate the median progression-free survival (PCWG3).
- To estimate the objective response rate (ORR) in those patients with measurable disease.
- To determine the safety/tolerability of rucaparib in a population of men with hormone sensitive prostate cancer.

Correlatives/Tertiary

- To measure the quantitative change in gamma-H2AX, RAD51, 53BP1 formation in tumor tissue following treatment with rucaparib (M1 disease only).
- To develop an RNA expression signature associated with response to rucaparib (M1 disease only).
- To estimate the percentage of patients with a loss-of-function mutation or total allelic loss of second somatic gene allele (i.e. LOH, or biallelic inactivation) (In all patients undergoing biopsy or with archived tissue).
- To investigate any association between PARP-1 and PARP-2 protein and mRNA expression levels in tumor with response to rucaparib (In all patients undergoing biopsy or with archived tissue).
- To examine the incidence of reversion mutations in circulating tumor DNA at clinical progression.

[figure not shown]

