**Study design**

The study is an open-label single arm Phase II trial. Eligible patients are those with metastatic hormone-sensitive prostate cancer (mHSPC) or high-risk biochemically recurrent prostate cancer (BCR). All patients must have a documented germline or somatic mutation in a homologous recombination DNA-repair gene (BRCA1, BRCA2, ATM, CHEK2, NBN, BRIP1, RAD50, RAD51C, RAD51D, PALB2, MRE11, FANCA, FANCB, FANCC, FANCD2, FANCE, FANCF, FANCG, FANCI, FANCL, FANCM). Germline genetic testing and molecular sequencing as a screening for eligibility will not be offered. A mandatory tumor biopsy will be performed prior to the start of therapy in all patients with metastatic disease (if tumor material is not successfully obtained at the time of biopsy, then archival material will be sought). A second, OPTIONAL tumor biopsy will take place after three months of therapy.

After enrollment, patients will be treated with rucaparib at the established dose of **600mg by mouth twice daily**. Patients will be followed monthly with clinic visits, safety labs (including CBC w/diff, Comp), PSA, and toxicity assessments. Treatment [with a minimum drug exposure of 12 weeks] will be continued until PSA progression (PCGW3 criteria) or clinical/radiographic progression (whichever comes first), or until unmanageable toxicity requiring drug cessation. Patients who remain on treatment

for >12 months can begin to have their clinic visits, safety labs (including CBC w/diff, Comp), PSA, and toxicity assessments every 3 months.

A trial schema for study treatment appears below:

Criteria for evaluation

Primary Endpoint

- PSA50 response rate, defined as a decline in PSA to  $\geq 50\%$  of baseline level, confirmed with a second measurement at least 4 weeks later (PCWG3).

Secondary Endpoints

- Safety/Tolerability, defined as incidence of CTCAE v5.0 grade  $\geq 3$  toxicities experienced by patients on the trial.
- PSA progression-free survival, defined as a time from initiation on rucaparib therapy until PSA increase of 25%, confirmed with another measurement at least 4 weeks later (PCWG3).
- Radiographic progression-free survival (PCWG3): time to radiographic or clinical progression or death, whichever comes first. Based on RECIST version

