### Exploratory Analyses

*Estimate the percentage of patients with a loss-of-function mutation or total allelic loss of second (somatic) gene allele (i.e. biallelic inactivation):*

The DNA mutations present in the tumor will be identified through Foundation Medicine sequencing. Patients with biallelic inactivation in an HRD gene(BRCA1, BRCA2, ATM, CHEK2, NBN, BRIP1, RAD50, RAD51C, RAD51D, PALB2, MRE11, FANCA, FANCB, FANCC, FANCD2, FANCE, FANCF, FANCG, FANCI, FANCL, FANCM) will be considered biomarker positive. For biomarker positive and biomarker negative subjects, we will calculate PSA50 response rates with confidence intervals for hypothesis generation.

*mRNA expression profile signature (positive and negative) and PSA50 response rates:*  
Subjects will have pretreatment tumor (or archived tissue) tested with mRNA expression profiling and scored for likelihood for response to rucaparib per the Decipher GRID platform (GenomeDx). For subjects considered to have a positive mRNA expression signature based upon a binary score assigned via the GenomeDx proprietary algorithm, a PSA50 response rate will be calculated. Similarly, a calculation will be performed for subjects considered to have a negative sRNA expression signature.

*PARP-1, PARP-2, γH2AX, RAD51, 53BP1 mRNA/protein levels:*

In patients that have biopsy-able disease, subjects will have pretreatment and on-treatment tumor biopsy specimens analyzed. IHC and RNA in situ hybridization staining

PARP-1 and PARP-2 will be performed on the pretreatment samples and scored on scale of 0 (none) to 3 (intense staining), and the results will be associated with responses for both proteins, separately, using descriptive statistics and Fisher's Exact Tests.

Immunofluorescence will be used to quantify the median intensity of each gH2AX, RAD51m and 53BP1 foci per cell as well determine the median number of foci per cell on the pretreatment biopsies. Using analytical microscopy, Drs. [name] and [name] have developed imaging software, which can isolate single nuclei and quantify both the intensity and number of immunofluorescent foci per nucleus (i.e. per cell). Using FFPE tissue obtained at biopsy, we will examine the change in DNA damage foci number and intensity (reported as median percent change) induced by PARPi in PSA50 responders versus non-responders using a T-test.

*Reversion Mutations:*

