### 2.3 Correlative/Exploratory/Tertiary Objectives

- To measure the quantitative change in gamma-H2AX, RAD51, 53BP1 formation in tumor tissue following treatment with rucaparib (only in patients undergoing biopsy).
- To develop an mRNA expression signature associated with response to rucaparib.
- To estimate the percentage of patients with a loss-of-function mutation or total allelic loss of second (somatic) gene allele (i.e. biallelic inactivation).
- To investigate any association between PARP-1 and PARP-2 protein and mRNA expression levels in tumor with response to rucaparib.
- To investigate any association between acquired reversion mutations with clinical progression on rucaparib.

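### The plan sets out to measure the change in DNA-damage foci after rucaparib, but its only inference compares responders with non-responders, and no overall within-patient change with an interval is specified.

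*Combined protocol and SAP*

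**What the plan says.** **Objective.** Section 2.3 lists first among the correlative objectives: "To measure the quantitative change in gamma-H2AX, RAD51, 53BP1 formation in tumor tissue following treatment with rucaparib". The synopsis repeats it, restricted to M1 disease. It is a before/after quantity and names no responder comparison.

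**Endpoint.** The synopsis list of exploratory endpoints asks a different question of the same markers: "To associate PSA response to rucaparib with changes in gamma-H2AX, RAD51, 53BP1 formation in tumor tissue compared to baseline".

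**Analysis.** Section 10.1.3.3 says "we will examine the change in DNA damage foci number and intensity (reported as median percent change", and the sentence goes on to the comparison "induced by PARPi in PSA50 responders versus non-responders using a T-test". The synopsis section on exploratory analyses has the same sentence. Neither place gives a confidence interval, a paired or one-sample analysis, or a significance level. Neither says whether the median percent change is taken over all pairs or within each response group.

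**Tissue.** The synopsis study design states: "A second, OPTIONAL tumor biopsy will take place after three months of therapy". The study calendar and section 5.2.2 limit biopsies to patients with metastatic disease, and a calendar footnote makes bone biopsy optional even before treatment. Section 10.1.3.3 opens by saying that pretreatment and on-treatment specimens will be analysed, but its quantification sentence refers only to the "median number of foci per cell on the pretreatment biopsies".

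**The concern.** The objective asks whether, and by how much, foci change within a man between the two biopsies. The planned t-test asks whether that change differs between PSA50 responders and non-responders. These are separate questions, and the second can have the answer no while the first has the answer yes. Replacing the t-test with a rank test would not help, because any between-group test is blind to a change common to both groups.

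Two things are at stake. A non-significant group comparison, being the only p-value attached to foci change, could be read as absence of a pharmacodynamic effect. And the objective would be answered at best by a median with no statement of uncertainty, from a small number of paired biopsies. Section 10.1.3.1, by contrast, promises confidence intervals for its exploratory response rates.

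**Working it through.** **1. The plan's own figures.** No sample size, SD, power or alpha is given for the foci analysis, so there is nothing there to reproduce. The only calculation in the documents is the Simon design for the primary endpoint (12 then 16 patients, stop at 6 or fewer, promising at 18 or more of 28). By exact binomial sums:
- early stopping at 50%: P(X ≤ 6 of 12) = 0.613, against 0.61 stated;
- type I error: 0.081, within the 0.1 stated;
- power at 75%: 0.902, against 90% stated.

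That calculation is sound and does not bear on this point.

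**2. What the planned test can see.** Let a man's change (for example the log ratio of on-treatment to pretreatment foci) have mean δR in responders and δN in non-responders, with SD σ. The two-sample t-test has noncentrality

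(δR − δN)/σ × √[nR·nN/(nR + nN)].

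If δR = δN = δ, this is 0 for every δ and every sample size, so the rejection rate is the nominal level. Simulation with 100,000 runs per setting, group sizes from 3+3 to 21+7 and shared changes of 0 to 1.5 SD gave 4.9% to 5.1% at two-sided 0.05, and 9.8% to 10.2% at two-sided 0.10. A skewed percent-change model gave about 4% at 0.05. Both alphas are assumptions.

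**3. What a paired analysis can see.** A one-sample t-test of the change over all n pairs has noncentrality (δ/σ)√n. At two-sided 0.05, with n and δ/σ assumed, the noncentral t gives:

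| Pairs | Shared 0.5 SD | Shared 1 SD | Planned test, either case |
|---|---|---|---|
| 6 | 17% | 51% | 5% |
| 10 | 29% | 80% | 5% |
| 12 | 35% | 88% | 5% |
| 15 | 44% | 95% | 5% |

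With 3, 4 or 5 pairs, power for a 1 SD change is only about 18%, 29% and 40%.

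**4. Precision of the estimate.** The 95% CI half-width in SD units is t(0.975, n−1)/√n:
- 6 pairs: 2.571/√6 = 1.05;
- 10 pairs: 2.262/√10 = 0.72;
- 15 pairs: 2.145/√15 = 0.55.

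**5. The planned test on its own question.** Assume about 75% responders and a 1 SD change in responders only. With groups of 6/2, 7/3, 9/3, 11/4 and 15/5, the formula in step 2 gives power of 18%, 25%, 27%, 36% and 45%. A non-significant result would therefore say little about a group difference, and nothing about the overall change.

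**The case against.** The strongest reply is that the t-test is the right test for its endpoint. Section 10.1.3 analyses the exploratory endpoints, and the foci endpoint is an association with PSA response. This stands: a reader might infer that the wrong test was chosen, but the documents do not support that. The gap is a missing analysis for a stated objective.

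Second, the objective is to measure, which is descriptive, and the documents state no null of zero change. A percent change between two biopsies from the same man is a within-patient quantity, so a change summary is planned. This also stands. A reader might infer that no estimate of change is planned at all, and the reference to median percent change rules that out. What remains open is whether the summary is pooled or by group, and how uncertain it is.

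Third, the 5% figure is not the plan's. The only alpha in the documents is the one-sided 0.1 for the primary endpoint. The general statement holds at any alpha.

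Fourth, a reader might infer from the larger pair counts in the table that a paired analysis would have good power. That is not established. Biochemically recurrent patients contribute no pairs and the second biopsy is optional, so fewer than 8 pairs is plausible. Nor is the gap between the table's columns a loss of power in the usual sense, since the two tests answer different questions.

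**Conclusion.** The point holds as a gap in the analysis plan, at low severity. The stated objective is the change after treatment; the plan gives an incompletely specified median and no interval, and its only inference cannot register a change shared by responders and non-responders. That test's rejection rate for a shared change equals its nominal level, whatever the size of the change. This follows from the test's null and does not depend on the number of pairs or the effect size.

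The paired-power figures do rest on assumptions that are not in the documents: the number of pairs, a normally distributed change of a given size in SD units, and two-sided 0.05. They show that the same tissue could address the objective directly, with precision ranging from poor to useful depending on how many men accept the second biopsy.

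The analysis is exploratory. Nothing here affects the primary endpoint or the go/no-go rule.

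**What to change.** In section 10.1.3.3 and the matching synopsis paragraph:

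- Add, as the analysis for the first correlative objective, the overall within-patient change from pretreatment to on-treatment tissue over all men with both biopsies. Do this for each of gamma-H2AX, RAD51 and 53BP1, and for both foci number and foci intensity: 3 × 2 = 6 outcomes.
- Report each with the number of pairs and a 95% CI, by a paired t analysis of the log ratio or by the signed-rank method with its interval. Name one in advance.
- State whether the median percent change is pooled, by response group, or both.
- Name the on-treatment biopsy in the foci quantification sentence.
- Keep the responder versus non-responder t-test for the association endpoint only, state its alpha and sidedness, and say that a non-significant group difference is not evidence that foci did not change.

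The cost is wording and six more exploratory estimates on data already to be collected, with no added patients, biopsies or assays. The estimates may be imprecise, and six outcomes raise the chance of an isolated positive finding, so they should be presented as estimates with intervals and labelled exploratory.
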